10.0 STATISTICAL METHODS

Administrative Summary

Between July 2016 and June 2017, institutional SSI rates were 29% and 9% for Whipple procedures and liver resections, respectively. Based on these lower than expected SSI rates we decided to compute the observed, overall infection rate among patients currently enrolled and treated on this trial to assess whether the trial hypotheses were reasonable assumptions. The current overall infection rate was estimated to be 11%. In addition, the observed percent of ineligible/non-evaluable patients was 14%. Consequently, the null and alternative hypotheses of the present trial are being amended from the previous null and alternative hypotheses of 30% and 15%, respectively to 17% and 5%, respectively, to reflect the overall, observed infection rate. The revised, maximum sample size will be inflated to reflect the observed percent of inevaluable patients, 14%. As of February 2018, 131 patients were randomized; no statistical analysis of the study endpoint has been conducted to date.

Revised Statistical Considerations

The primary study endpoint is SSI rate. Patients will be stratified by surgical site (colorectal vs hepatopancreatobiliary) and BMI (<30 vs ≥30), and randomly assigned to conventional wound care group or negative wound pressure group with 1:1 allocation. The hypothesized SSI rate is 17% for the conventional wound care group (control group) [1]. We anticipate a reduction of the rate to 5% in the negative wound pressure group (experimental group).

As this is a phase II study, a larger type I error rate of 0.1 will be used. Based on a chi-square test comparing two-sample binomial probabilities at a 1-sided significance level of 0.1, the study has approximately 85% power to detect the difference in SSI rates between 17% in the control

group and 5% in the experimental group. With the allowance of 14% ineligible/non-evaluable patients (based on the observed percentage of evaluable patients to date), up to 170 patients (85 per arm) will be enrolled. Given that 143 patients have already enrolled on the study, up to 27 additional patients will be accrued to meet the revised, maximum study sample size.

With an accrual rate of 4 patients per month, we expect to complete the additional accrual in less than 8 months.

Preoperative, intraoperative, and postoperative variables will be prospectively collected.

10.1 STATISTICAL ANALYSIS

The primary analysis will include all randomized and evaluable patients but exclude ineligible patients or patients who are canceled from the study before receiving any wound care. SSI is defined as an infection that occurs within 30 days of operation. The primary endpoint is the SSI rate. The primary analysis of comparing the conventional wound care (control group) and the incisional V.A.C® (experimental group) will be conducted using a chi-square test for two-sample binomial probabilities with a one-sided significance level of 0.1. The observed SSI rates and 90% Upper Confidence Bound (UCB) estimates will be reported. Preoperative, intraoperative, and postoperative variables will be tabulated and appropriate summary statistics will be reported. As a secondary analysis, comparison of treatment groups for SSI will be adjusted for any significant preoperative, intraoperative, or postoperative variables using logistic regression.

For secondary endpoints, the incidence of SSI as superficial incisional, deep incisional, and organ/space will be estimated along with the 90% UCBs. The secondary endpoint length of stay is a continuous variable. A Wilcoxon rank sum test will be used to assess the significance of the difference between groups in median length of stay. Median length of stay, its range and quartiles will be reported.

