5.0 STUDY DESIGN

5.1 STUDY DESCRIPTION

This study is a multi-center, open-label, randomized clinical trial conducted at Duke Cancer Institute and Indiana University to evaluate whether incisional NPWT can help reduce the rate of SSI in patients undergoing either colorectal or hepatopancreatobiliary surgery. Up to 170 subjects will be randomized in a 1:1 ratio to either conventional wound care (control group) or the incisional NPWT (experimental group) to ensure 138 evaluable subjects.

The primary study endpoint will be SSI within the laparotomy wound, as assessed on postoperative day 4-5 and the first postoperative clinic visit, which is anticipated to be within 30 days of surgery. Evaluable subjects are defined as those who have been randomized and completed both postoperative assessments. Non-evaluable subjects are those subjects who were randomized but did not complete both post-op visits. Non-evaluable scenarios include aborted surgeries, cancelled surgeries, death unrelated to study, and early device removal related to device malfunction. Screen failures are defined as those subjects not randomized.

Safety endpoints will be adverse events related to the device or dressing, including the presence of any abnormal skin findings (such as blisters or rash). These endpoints will be assessed from the day of surgery through the 30-day follow-up visit.

Subjects randomized to conventional wound care (control group) will have their skin incisions closed with skin staples, sutures, or surgical glue (per judgment of the treating physician), covered with sterile medical gauze and a form of adherent (tape or clear adhesive) for which the subject does not have any allergy. This dressing will be removed per the treating physician's discretion or institutional standards.

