5.2 RANDOMIZATION

Subjects who meet all inclusion criteria and no exclusion criteria and who consent to participate in the study will be randomized in a 1:1 ratio to receive either incisional NPWT via PIMS or ActiV.A.C or the standard-of care dressing following surgery. Randomization may occur up to 5 business days prior to surgery. If a subject is randomized and surgery is subsequently delayed, they will not be re-randomized even if outside the 5-day window.

Randomization will be stratified according to surgical site (colorectal vs hepatopancreatobiliary) and body mass index (BMI), < 30 vs ≥ 30.

Randomization using permuted block scheme will be done via REDCap Randomization Application. Please refer to the randomization manual for detailed instructions.

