6.0 SUBJECT SELECTION

6.1 INCLUSION CRITERIA

1. Female and male patients 18 years of age or older
2. Scheduled for an elective surgery in either open CRS or open HPBS. This includes, but is not limited to: ileocecectomy, right hemicolectomy, extended right hemicolectomy, transverse colectomy, left hemicolectomy, sigmoidectomy, proctectomy, low anterior resection or abdominoperineal resection, hepatectomy, bile duct reconstruction, duodenectomy, pancreatectomy, pancreaticoduodenectomy, or pancreatic duct reconstruction

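### The primary chi-square ignores the stratification factors and procedure type, so a chance imbalance in Whipple cases within the hepatopancreatobiliary stratum would go uncorrected; overall type I error is not affected

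*Combined protocol and SAP*

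**What the plan says.** - **Primary test (10.1).** The comparison of arms "will be conducted using a chi-square test for two-sample binomial probabilities with a one-sided significance level of 0.1". No covariate or stratum enters it.
- **Randomisation (5.2).** "Randomization will be stratified according to surgical site (colorectal vs hepatopancreatobiliary"); the same sentence adds BMI below 30 versus 30 or more as a second factor. Section 10.0 repeats both factors.
- **Case mix (6.1).** Patients are "Scheduled for an elective surgery in either open CRS or open HPBS". The list of operations puts liver, bile duct and pancreatic surgery, including pancreaticoduodenectomy, on the hepatopancreatobiliary side. The operation is booked before randomisation.
- **Risk by operation (10.0).** From July 2016 to June 2017, "institutional SSI rates were 29% and 9% for Whipple procedures and liver resections, respectively". The pooled SSI rate in the trial was estimated at 11%.
- **Adjusted analysis (10.1).** A secondary logistic regression adjusts for whichever preoperative, intraoperative or postoperative variables prove significant. It names neither procedure nor the stratification factors.
- **Timing (10.0).** 143 of at most 170 patients are enrolled, and the plan states that the endpoint has not yet been analysed statistically.

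**The concern.** By the plan's own figures, SSI risk differs about threefold between two operations in the same randomisation stratum. Nothing in the design balances them between arms, and the primary test does not allow for a difference.

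The trial will turn on few events. At 11%, 146 evaluable patients (170 × 0.86) yield about 16 SSIs. A split of 11 v 5 is positive at one-sided 0.1 and a split of 10 v 6 is not. If one arm happens to receive several more Whipples, the primary test cannot separate that from an effect of the dressing. With only 27 patients still to enrol, changing the stratification now would do little; the analysis is where this can be addressed.

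**Working it through.** **1. The plan's power figure.** Inputs: "The hypothesized SSI rate is 17% for the conventional wound care group (control group"); "We anticipate a reduction of the rate to 5% in the negative wound pressure group (experimental group"); one-sided 0.1; 69 per arm, from the aim in 5.1 "to ensure 138 evaluable subjects". Section 10.0 says "the study has approximately 85% power to detect the difference in SSI rates between 17% in the control" group and 5% in the experimental group.

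- SE under the null = √(2 × 0.11 × 0.89 / 69) = 0.0533
- SE under the alternative = √(0.17 × 0.83/69 + 0.05 × 0.95/69) = 0.0523
- Power = Φ[(0.12 − 1.2816 × 0.0533)/0.0523] = Φ(0.989) = 83.9%

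Exact enumeration gives 86.3%, and 73 per arm gives 85.4% by the formula. The stated figure reproduces, so the planned test is the uncorrected, unadjusted chi-square.

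**2. How few events decide it** (73 per arm, 16 events, pooled rate 0.1096, SE = √(0.1096 × 0.8904 × 2/73) = 0.0517).

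- 11 v 5: z = (6/73)/0.0517 = 1.59, p = 0.056
- 10 v 6: z = (4/73)/0.0517 = 1.06, p = 0.145

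**3. Effect of a given imbalance.** With m more Whipples in control than in NPWT and no treatment effect, the expected difference in rates is (0.29 − 0.09) × m/69. With average risk 0.17, SE = √(2 × 0.17 × 0.83/69) = 0.0640. One-sided error = 1 − Φ(1.2816 − shift/SE), or with a plus sign if the excess is in NPWT.

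| m | shift | shift/SE | error, excess in control | error, excess in NPWT |
|---|---|---|---|---|
| 4 | 0.0116 | 0.181 | 0.136 | 0.072 |
| 6 | 0.0174 | 0.272 | 0.156 | 0.060 |
| 8 | 0.0232 | 0.363 | 0.179 | 0.050 |
| 11 | 0.0319 | 0.499 | 0.217 | 0.038 |

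**4. How often such imbalances occur.** The Whipple split within the stratum is hypergeometric. Example: 138 patients, all hepatopancreatobiliary, 55 of them Whipples (40%). Average risk is (55 × 0.29 + 83 × 0.09)/138 = 17.0%, matching the design's control rate. The control count has SD √[69 × (55/138) × (83/138) × (69/137)] = 2.89, so the difference between arms has SD 5.8. An excess of 11 (33 v 22) is the 97.5th percentile.

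Exact conditional error of the unadjusted test, 69 per arm, all hepatopancreatobiliary:

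| Whipple share (assumed) | 2.5th percentile | 97.5th percentile | averaged over all splits |
|---|---|---|---|
| 10% | 0.055 | 0.174 | 0.106 |
| 25% | 0.036 | 0.214 | 0.104 |
| 40% | 0.034 | 0.212 | 0.103 |
| 50% | 0.035 | 0.204 | 0.101 |
| 75% | 0.044 | 0.185 | 0.101 |

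At the 16th and 84th percentiles the error is about 0.055–0.068 and 0.136–0.160. If half the patients are colorectal (assumed SSI 15%) and 25–50% of the rest are Whipples, the outer range narrows to about 0.044–0.19.

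**5. Mixed populations.** Simulations with 146 evaluable patients, balance within site and BMI and five assumed mixes gave 0.16–0.18 in the 12–19% of randomisations with most Whipples in control, and 0.05–0.06 in the opposite tail. A second set of mixes, with up to 68% colorectal at an assumed 15%, gave 0.15–0.17 and 0.05–0.07.

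**6. Stratified test.** For stratum i, with control events xᵢ, total events tᵢ and sizes n₁ᵢ + n₂ᵢ = nᵢ: z = Σ(xᵢ − tᵢn₁ᵢ/nᵢ) / √Σ[tᵢ(nᵢ − tᵢ)n₁ᵢn₂ᵢ / (nᵢ²(nᵢ − 1))].

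- Stratified by procedure, its error is about 0.10 overall and 0.094–0.102 in the tails where the unadjusted test gives about 0.19–0.23 or 0.03–0.05.
- Average power at a common risk ratio of 5/17 and 40% Whipples is 86.5%, against 86.3% unadjusted.
- In the 14–19% of randomisations with most Whipples on NPWT, power is 79–90% stratified, against 75–85% unadjusted.
- The two tests reach different decisions in about 3–4% of trials.

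**The case against.** An unadjusted chi-square that matches the sample-size calculation is valid and common in phase II. A reader might infer from the 29% and 9% that the trial's error rate is doubled or halved. The documents do not support that: over all randomisations the error stays at 0.098–0.106. A conditional error of 0.20 or more has probability 1–4% if all patients are hepatopancreatobiliary and under 1% if half are. That objection stands.

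A reader might also infer that only colorectal versus hepatopancreatobiliary is balanced. BMI is balanced too, although that does nothing for Whipple versus liver.

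The plan does have an adjusted analysis, so an imbalance would not go unexamined. That is true, but its covariates are picked by significance, it may condition on postoperative variables that the dressing could affect, and procedure is not named. If it disagreed with the chi-square, the plan offers no basis for preferring it.

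The inputs are also soft. The 29% and 9% are one year of institutional rates without denominators, in a two-centre trial, and the case mix is not given. With no treatment effect and only hepatopancreatobiliary patients, the pooled 11% implies 0.09 + 0.20w = 0.11, so w = 10% Whipples, where the tail range is 0.055–0.174. But 11% is also the mean of 17% and 5%, so it does not establish a low Whipple share.

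**Conclusion.** The concern holds as a matter of robustness. The primary test leaves out both stratification factors and a strong baseline risk factor that the plan itself quantifies. Conditional on imbalance, the one-sided error is about 0.16–0.18 or 0.05–0.06 in the most imbalanced 12–19% of randomisations on either side (about 6–8 more Whipples in one arm). It approaches 0.20 or 0.035 only in the outer 2.5% tails.

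This rests on the institutional 29% and 9% applying to the trial, an assumed Whipple share of 10–40% and an assumed colorectal rate of 11–17%. The effect shrinks as the colorectal share rises. It is neither a loss of type I error control nor a flaw in the power calculation.

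**What to change.** Before any by-arm look:

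1. In 10.1, make the primary test a one-sided 0.1 Cochran-Mantel-Haenszel test stratified by scheduled procedure group (colorectal / pancreatic / liver-biliary, fixed from the booking made before randomisation) and BMI stratum (<30 v ≥30). Keep the unadjusted chi-square as a supporting analysis.
2. In the secondary logistic regression, replace selection by significance with these prespecified baseline factors.

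**Cost.** Each operation listed in 6.1 must be assigned to a group in advance, and the group derived from the booked operation. The documents do not list that as a recorded field, so its availability should be confirmed. The 29% is for Whipple only and no rates are given for other pancreatic or biliary operations; the stratified test is valid whatever those rates are, but gains less if risk varies within a group. No extra patients are needed and average power stays within about 1 point.

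The real drawback is timing: the primary test of an open-label trial would change with 143 of 170 enrolled and the pooled rate known. The amendment should state that no endpoint analysis had been done and that the pooled rate was the only outcome information seen, if that is still so.

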4.0 STUDY OBJECTIVES

4.1 PRIMARY

- To compare the incidence of SSI rates between conventional wound care versus the incisional NPWT via PIMS or ActiV.A.C. within CRS or HPBS-associated laparotomy wounds as assessed on postoperative day 4-5 and the first postoperative clinic visit.

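### Section 10.1 plans no interval for the between-arm difference in SSI, and lets undefined significance choose the covariates of the secondary model (minor)

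*Combined protocol and SAP*

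**What the plan says.** Section 4.1 sets a between-arm objective: "To compare the incidence of SSI rates between conventional wound care versus the incisional NPWT via PIMS or ActiV.A.C".

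Section 10.1 gives the primary analysis as a comparison "conducted using a chi-square test for two-sample binomial probabilities with a one-sided significance level of 0.1". The estimates that go with it are in one sentence: "The observed SSI rates and 90% Upper Confidence Bound (UCB) estimates will be reported". No section names a risk difference, risk ratio or odds ratio, or an interval for any contrast between the arms.

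For the secondary analysis, section 10.1 says that "comparison of treatment groups for SSI will be adjusted for any significant preoperative, intraoperative, or postoperative variables using logistic regression". It gives no threshold for significance and no selection method.

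Section 5.2 stratifies randomisation by surgical site and by BMI below 30 v 30 or more, and section 10.0 repeats this: "Patients will be stratified by surgical site (colorectal vs hepatopancreatobiliary) and BMI". Section 10.1 does not mention these factors. As preoperative variables they reach the adjusted model only through the significance rule.

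**The concern.** Section 10.0 justifies its alpha by the trial's phase: "As this is a phase II study, a larger type I error rate of 0.1 will be used". Readers of such a trial must judge whether the benefit is worth pursuing, and for that they need the range of differences that the data allow as well as the test result. An upper bound on each rate does not supply it. A lower limit for control minus negative pressure wound therapy (NPWT) needs a lower limit on the control rate, and none is planned. If the interval is left out of the plan, its level and form can be settled after the result is known.

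The covariate rule raises two separate problems. Factors that were important enough to stratify on may be kept or dropped by chance in a small trial. The rule also admits postoperative variables. These arise after the dressing is applied and may be affected by it, so adjusting for them can remove part of the effect being estimated.

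**Working it through.** **Inputs.** Rates of 17% v 5%, one-sided alpha 0.1, power of about 85%, 170 enrolled, a 14% non-evaluable allowance and a pooled SSI rate of 11% to date (section 10.0); 138 evaluable (section 5.1). Evaluable per arm: 138/2 = 69, or 170 × 0.86 ≈ 146 and 146/2 = 73. Expected infections: 0.11 × 138 ≈ 15, or 0.11 × 146 ≈ 16. The splits between arms below are assumed.

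**The plan's own figure.** Power = Φ[(0.12 − 1.2816·SE₀)/SE₁], where SE₀ uses the pooled rate of 11% and SE₁ the separate rates.
- 69 per arm: SE₀ = 0.0533, SE₁ = 0.0523, power 83.9%.
- 73 per arm: SE₀ = 0.0518, SE₁ = 0.0508, power 85.4%.

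The stated figure reproduces. Exact enumeration of the same test gives 86.3% and 87.8%.

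**What the plan would report, and what it would not.** Take 12/73 v 4/73, the split of 16 infections nearest the planning rates.
- Test: the pooled rate is 16/146 = 0.1096 and its SE 0.0517, so Z = 0.1096/0.0517 = 2.12 and one-sided p = 0.017.
- Planned output: 16.4% and 5.5%, with exact (Clopper-Pearson) one-sided 90% upper bounds of 23.4% and 10.7%. Subtracting the bounds gives 23.4 − 10.7 = 12.7 points, which is not a limit for anything.
- Missing output: the difference is 0.1644 − 0.0548 = 0.1096. The Wilson limits at z = 1.2816 are 0.1163 to 0.2272 (control) and 0.0294 to 0.0997 (NPWT).
  - Newcombe lower limit: 0.1096 − √[(0.1644 − 0.1163)² + (0.0997 − 0.0548)²] = 0.044.
  - Newcombe upper limit: 0.1096 + √[(0.2272 − 0.1644)² + (0.0548 − 0.0294)²] = 0.177.

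The result is 11.0 points, 80% CI 4.4 to 17.7. The same method for other splits gives:

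| Control v NPWT | One-sided p | Difference (points) | 80% CI |
|---|---|---|---|
| 11/73 v 5/73 | 0.056 | 8.2 | 1.6 to 15.0 |
| 10/69 v 5/69 | 0.086 | 7.2 | 0.4 to 14.2 |
| 11/69 v 4/69 | 0.028 | 10.1 | 3.4 to 17.1 |

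**Does the interval compete with the test?** By exact enumeration at true rates of 17% v 5%, the 80% interval includes zero in 0% (69 per arm) to 1.1% (73 per arm) of positive trials. Its mean width in those trials is 13.6 and 13.2 points. So it agrees with the one-sided 0.1 decision.

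**Covariate rule (simulation).** The documents give neither the cut-off nor the strength of the factors. Assumed: a 0.05 cut-off, risk ratio 2 for each factor, half the patients in each surgical site, 35% or 50% in the higher-risk BMI group, 138 or 146 evaluable.
- The rule keeps neither factor in 47% to 54% of trials, one in 39% to 44% and both in 7% to 9%. A second, more approximate simulation put neither at about 59%.
- The adjusted odds ratio differs from that of the always-adjusted model by a median of about 2%, with a 90th percentile of about 6%.

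**Would a stratified primary test matter?** Replacing the crude test by a Cochran-Mantel-Haenszel test changed simulated power by −0.2 to +0.6 points and the decision in 0.9% to 1.7% of trials.

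**The case against.** The strongest reply is that little is lost. The observed rates are reported, so the size of the effect follows by subtraction. With the denominators, any reader can rebuild the 2×2 table and compute an interval. The method hardly matters: for 10/69 v 5/69 the 80% interval is 0.4 to 14.2 points by Newcombe and 0.5 to 14.0 by Wald. The one-sided 0.1 framework already points to the matching level. The adjusted model is labelled secondary, the simulated effect of dropping the strata is small, and the simulation rests on assumed inputs. Finally, the plan never says outright that the upper bounds are per arm.

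Most of this stands, and it is why the point is minor. It does not remove the gap: the precision of the contrast is nowhere planned, and choosing it later is avoidable. The per-arm reading is an inference, but the sentence attaches the bounds to the rates and not to a difference. The small effect of dropping the strata says nothing about the admission of postoperative variables.

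A reader might infer more than the documents support:
- That the crude chi-square test is invalid because randomisation was stratified. It is the test used for the sample size, and stratifying it changes almost nothing.
- That the trial will not show how large the effect is. The two rates show it.
- That the selection rule seriously distorts the adjusted odds ratio through the strata. The figures above do not show that.

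**Conclusion.** The point holds as a minor improvement to reporting and to the secondary analysis. Section 10.1 gives no interval for the comparison that section 4.1 sets as the objective. Upper bounds alone cannot give a lower limit for the benefit. At 15 to 16 infections the missing 80% interval is about 13 points wide when the trial is positive, so it carries real information. In the secondary model, significance selection can drop the randomisation factors by chance and can admit postoperative variables. The first of these has a small effect, and the second was not quantified.

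The primary test, alpha, sample size, power and decision rule are not in question. The interval examples rest on assumed splits of the infections, and the width on the planning rates of 17% v 5%. The covariate figures rest on an assumed cut-off, risk ratios and stratum shares.

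**What to change.** Keep the one-sided 0.1 chi-square test as the primary analysis and make two changes in section 10.1.

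1. Add:
> The treatment effect will be reported as the crude risk difference (control minus NPWT) with a two-sided 80% Newcombe interval, matching the one-sided 0.1 test.

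2. Replace the covariate rule with:
> The secondary logistic regression will include treatment, surgical site and BMI group whatever their significance, with no covariates selected by significance and no postoperative variables; the adjusted odds ratio will be reported with an 80% interval, using a Firth-penalised fit if the ordinary fit fails or separates.

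One measure at one level is enough. A risk ratio, a Mantel-Haenszel difference, duplicate 95% intervals or an added Cochran-Mantel-Haenszel test would bring back a choice among results and gain almost nothing.

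The cost is plan wording and a few lines of code. The strata are recorded at randomisation, and section 10.0 states that the endpoint had not been analysed when the plan was revised. The downside is imprecision. With about 16 events and three model terms there are roughly 5 events per term, and the standard error of the log odds ratio is about 0.65. The 80% interval would then run from the estimate divided by 2.3 to the estimate times 2.3 (exp(1.2816 × 0.65) = 2.3). In about 3% to 5% of simulated trials the ordinary fit failed or gave extreme coefficients, hence the named fallback.

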1.0 INTRODUCTION

Surgical Site Infection (SSI) is a major source of morbidity in both colorectal (CRS) and hepatopancreatobiliary (HPBS) surgery. The SSI rate has been published to be between 20-35% [1-3]. Specifically, colectomy for the treatment of colorectal cancer is associated with a SSI rate of 10-30% [1] and hepatectomy for hepatocellular carcinoma has a SSI rate of 15-25% [4, 5]. Pancreaticoduodenectomy for pancreatic adenocarcinoma has a SSI rate of 10-20% [2, 6]. Taken together, up to a third of patients undergoing these complex abdominal surgeries will suffer the additional morbidity of SSI despite interventions such as appropriately timed and selected antibiotics. This added level of morbidity increases the complexity of patient care during recovery from surgery, lengthens post-operative hospitalizations and adds significant overall medical costs. Given these persistently high rates of SSI despite best practice standards, a low morbidity intervention such as the incisional wound vacuum assisted closure (V.A.C) system is an attractive technology to try to further improve SSI rates in these patients.

V.A.C® technology or negative pressure wound therapy (NPWT) has revolutionized the management of complex open wounds but its role in closed wounds remains undefined. Initial enthusiasm for its potential role in reducing SSI rates in closed laparotomy wounds came from a report in the cardiothoracic literature performed as a collaboration between Duke University Medical Center (DUMC) and the Durham VA Medical Center [7]. Negative pressure wound therapy was applied to closed sternotomy wounds in 57 patients, with a 3% expected SSI rate. No sternal wound infections were seen in any patients. Though this initial report had small numbers of patients, the potential for this low morbidity technique to decrease SSI in sternotomy wounds was seen.

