Subjects randomized to the incisional NPWT (experimental group) will have their skin incisions closed with skin staples or sutures (per judgment of the treating physician), a layer of non-adhesive dressing (Adaptic: Johnson & Johnson, New Brunswick, New Jersey) will cover the skin staples or sutures, followed by placement of an adhesive (Benzoin: generic), a Prevena™ Incision Management System peel and place or customizable dressing (KCI USA, Inc, San Antonio, Texas) covering only the skin staples or sutures. Please note, surgical glue should not be used for the experimental group. NPWT will be delivered using either the Prevena pump or the ActiV.AC. The incisional NPWT will then be continued for a minimum of 2 days up to a maximum of 7 days depending on physician preference.

Subjects will be clinically managed according to routine standard of care. Subjects will be assessed during their inpatient stay and at the time of routine postoperative clinic visits which is anticipated to be within 30 days of discharge. Presence or absence of SSI will be determined on postoperative day 4-5 and again at the time of the postoperative clinic visit, which is anticipated to be within 30 days of discharge. Criteria for determination of SSI are listed in Section 8.

Patients who are candidates for a laparoscopic approach will not be recruited. Note: patients scheduled for a staging laparoscopy followed by an open procedure are permitted to participate.

See Appendix 1 for the study schema.

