11.0 INVESTIGATIONAL PRODUCT

The PIMS and ActiV.A.C. therapy units and associated dressings will be supplied by KCI.

Incisional NPWT will be removed prior to hospital discharge.

In the event that the clinician or study designee encounters issues with PIMS or control dressings prior to the desired time for removal, dressing replacement/reinforcement is acceptable but must be documented in the case report form (CRF). The PIMS unit may also be switched to use an ActiV.A.C unit. Any loss of negative pressure will be documented and will not determine subject evaluability. Please refer to the PIMS Instructions manual for guidance on operational questions.

A PIMS canister filled with 45 mL of wound fluid will lead to a “canister full” alarm.

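### The secondary adjusted SSI comparison admits any significant postoperative variable, so it can adjust for something that the treatment arm or the infection itself affects

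*Combined protocol and SAP*

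**What the plan says.** Section 10.1 makes an unadjusted chi-square test at one-sided 0.1 the primary analysis. It then adds, as a secondary analysis, that "comparison of treatment groups for SSI will be adjusted for any significant preoperative, intraoperative, or postoperative variables using logistic regression". The only other description of the candidates is in Section 10.0: "Preoperative, intraoperative, and postoperative variables will be prospectively collected". Section 10.1 also says they will be tabulated. No section names them or gives a test or threshold for significance. Nor is it said whether the significance is for association with SSI or with arm.

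Other parts of the plan bear on which variables this rule can reach:

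- **Timing.** Section 5.2: "Randomization may occur up to 5 business days prior to surgery". Intraoperative and postoperative variables therefore arise after randomisation.
- **Length of stay.** Section 10.1: "The secondary endpoint length of stay is a continuous variable". It is compared by arm. Section 1.0 says that SSI "lengthens post-operative hospitalizations and adds significant overall medical costs". Section 11.0 adds: "Incisional NPWT will be removed prior to hospital discharge".
- **Closure method.** Section 5.1 allows glue in the control arm, but "surgical glue should not be used for the experimental group".
- **Stratification.** Section 5.2 stratifies by surgical site and by BMI below 30 or not.

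**The concern.** Adjustment for variables fixed before randomisation removes chance imbalance. Adjustment for a variable that the arm affects removes part of the treatment effect. If the variable results from both arm and SSI, conditioning on it creates an association that randomisation had ruled out.

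Selection by significance makes this more likely. A screen on association with SSI favours the consequences of SSI, and a screen on difference between arms favours variables that the arm changes. With about 15 events expected, such selection is also unstable.

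This is the plan's only adjusted estimate of the treatment effect on SSI. If it disagreed with the primary result, a reader could not tell whether confounding had been removed or bias introduced.

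**Working it through.** **Inputs from the documents.** SSI 17% and 5%, pooled observed rate 11%, 14% ineligible or non-evaluable, maximum 170 enrolled (Section 10.0); 138 evaluable (Section 5.1). Every covariate effect below is assumed, because the documents give none.

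**The plan's own figure.** The one-sided 0.1 chi-square test with pooled variance has power 0.839 at 69 per arm (138 evaluable) and 0.854 at 73 per arm (170 × 0.86 = 146). The stated power of about 85% reproduces. The concern does not depend on it.

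**Events and unadjusted effect.** 69 × 0.17 + 69 × 0.05 = 15.2 events; 0.11 × 138 = 15.2. The odds ratio is (0.05/0.95)/(0.17/0.83) = 0.257.

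**(a) Length of stay.** Let log stay be normal with SD s. SSI multiplies stay by D, and NPWT multiplies it by G at a given SSI status. By Bayes' rule:

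adjusted OR = OR × exp(−ln D × ln G / s²)

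With D = 1.5 and s = 0.5:

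| G | Multiplier | Adjusted OR, 17% vs 5% | Adjusted OR, no SSI effect |
|---|---|---|---|
| 0.8 | 1.436 | 0.369 | 1.436 |
| 0.9 | 1.186 | 0.305 | 1.186 |
| 1.0 | 1 | 0.257 | 1 |
| 1.1 | 0.857 | 0.220 | 0.857 |
| 1.2 | 0.744 | 0.191 | 0.744 |

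Over D from 1.3 to 2.0 and s from 0.4 to 0.6, the adjusted OR runs from 0.277 to 0.406 for G = 0.9 at 17% vs 5%. It runs from 0.66 to 0.93 for G = 1.1 with no SSI effect. The row G = 1 shows that a variable depending on SSI alone leaves the odds ratio unchanged.

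**(b) Mediator.** Take logit P(SSI) = a + bT + cM, with M present in 40% of controls. Solve a and b so that the marginal risks are 17% and 5%; exp(b) is the adjusted odds ratio.

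| M in NPWT arm | Mediator OR | Adjusted OR |
|---|---|---|
| 30% | 4 | 0.282 |
| 20% | 6 | 0.357 |
| 15% | 10 | 0.459 |

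**(c) The rule applied.** Simulation with 69 per arm and 4,000 replicates: a univariable screen at two-sided 0.05 (threshold assumed), then plain logistic regression on treatment plus the variable if selected.

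| Case | Variable selected | Median adjusted/unadjusted OR |
|---|---|---|
| Stay, G = 0.9, 17% vs 5% | 0.866 | 1.145 |
| Stay, G = 0.8, 17% vs 5% | 0.900 | 1.402 |
| Stay, G = 1, 17% vs 5% | 0.823 | 1.000 |
| Stay, G = 1.1, 11% vs 11% | 0.798–0.815 | 0.891 |
| Stay, G = 1.2, 11% vs 11% | 0.798–0.815 | 0.773 |
| Mediator OR 4 | 0.735 | 1.044 |
| Mediator OR 6 | 0.920 | 1.358 |
| Mediator OR 10 | 0.960 | 1.741 |

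**(d) Closure with glue.** No protocol-compliant NPWT patient has glue, so treatment plus glue fits three cells exactly. The treatment odds ratio then compares NPWT with glue-free controls only. Assume glue in 30% of controls.

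- SSI with glue 10%: without glue (0.17 − 0.3 × 0.10)/0.7 = 0.200, OR 0.211.
- SSI with glue 25%: without glue (0.17 − 0.3 × 0.25)/0.7 = 0.136, OR 0.335.

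**(e) The proposed model.** Treatment, site and BMI group, assuming 50% in each site group, 35% with BMI of at least 30, and site/BMI odds ratios of 1/1, 2/2 and 4/3. Median estimates are 0.257, 0.239 and 0.218 against true values of 0.257, 0.250 and 0.234. The fit failed to converge in 4.1%, 2.9% and 5.6% of trials, against 2.5–4% without covariates. The chance of no events in the NPWT arm is 0.95^69 = 0.029.

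**The case against.** The strongest reply is that the model is secondary, has no alpha or decision role in a phase II trial, and would be reported beside the unadjusted rates. That is right, and it limits the weight of the point.

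Several narrower objections also have force:

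- **Stay is an endpoint with its own Wilcoxon test, so an analyst might never treat it as a covariate.** True, but the sentence directs adjustment for any significant postoperative variable and does not exclude stay.
- **G is the arm's effect on stay at a given SSI status.** Fewer infections alone would shorten geometric mean stay by about 5% (1.5 to the power −0.12 = 0.95) without moving the odds ratio. The one mechanism in the documents, device removal before discharge, points if anything to a longer stay, and weakly, since removal is allowed after 2 days. The shortening rows are therefore assumption only.
- **The 0.211 glue case would rarely arise under a p < 0.05 screen.** In simulation, glue was selected in 2–9% of trials when SSI with glue was 10%, and in 51–57% when it was 25%. This stands.
- **The milder shifts are small against noise.** The standard error of the log odds ratio is about 0.64, an approximate 95% range of 0.07 to 0.90 around 0.257. This stands, but the shifts are systematic, whereas the noise is not.
- **Adjusted and unadjusted odds ratios can differ without bias.** The true values in (e) show this. With fixed baseline terms, however, the reader knows the source of the difference.
- **Most intraoperative variables precede the dressing.** The risk from them is weaker, and excluding them has a cost.

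**Conclusion.** The concern holds. As written, the rule can adjust for variables affected by the arm or by SSI, and nothing elsewhere in the document restricts it. The examples are possible covariates, not planned ones.

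The size depends wholly on assumed covariate effects. It ranges from negligible (median ratio 1.04 for the weakest mediator) to substantial (1.74 for the strongest), and the bias can run either way. With no treatment effect on SSI, a stay lengthened by NPWT would produce an apparent benefit of 0.86 or 0.74.

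Only the secondary model is affected. The wording should be changed, but the trial's main inference does not depend on it.

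**What to change.** Replace the sentence in Section 10.1 with:

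> As a secondary analysis, SSI will be compared between groups by logistic regression with treatment and the stratification factors, surgical site and BMI group (<30 vs ≥30), as fixed terms. Any further covariate will be measured before randomisation and named before the outcome is analysed by arm; no covariate is selected by significance, and no postoperative variable or variable set by the arm is included.

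Keep intraoperative and postoperative variables in the tables by arm, and leave the primary chi-square test as it is. A penalised fit is optional, for an arm or stratum with no events. If it is wanted, the method and its trigger should be written into the plan in advance.

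The cost is one sentence, since site and BMI group are already held for randomisation. The model gives up adjustment for chance intraoperative imbalance, which the tables still show. Concomitant medication first recorded on the day of surgery (Section 7.2 allows this) could not be used if randomisation came earlier. Some 3–6% of plain three-term fits may fail to converge, slightly more than without covariates. Section 10.0 says that no analysis of the endpoint had been done at the time of the amendment, so a change then could be made without knowledge of results by arm.
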